3. STUDY DESIGN

This study is a Phase 2b/3, two arm, randomized, double blind, placebo controlled, adaptive design study to evaluate the safety and efficacy of leronlimab (PRO 140) in patients with severe or critical symptoms of respiratory illness caused by Coronavirus disease 2019 (COVID-19). Patients will be randomized 2:1 to receive leronlimab (PRO 140) or placebo. Subjects will receive weekly 700 mg leronlimab (PRO 140) or placebo via subcutaneous injection for two weeks. The study will enroll 390 subjects.

A single arm, non-randomized, open-label phase is added to the protocol after completion of enrollment in the Randomized Phase of the study. Up to 100 subjects will be enrolled in the non-randomized phase.

The study flow diagram is presented in Figure 3-1.

◆Up to 4 Weeks SCREENING PERIOD Screening Visit Visit 1 (V1) Subject Meet Screen Inclusion/Exclusio Failure Yes Visit 2 (V2) Day 0
Within 7 Days of Screening Visit First Leronlimab dose TREATMENT PERIOD Visit 3 (V3) Day 3 Up to 2 Weeks 3 (±1) days after V2 Visit 4 (V4) **Day 7**7 (±1) days after V2 Second Leronlimab dose Visit 5 (V5) / EOT **Day 14** 7 (±1) days after V4 Visit 6 (V6) (14 ± 3 Days after EOT Visit) FOLLOW-UP PERIOD V6 to V7 Visits Visit 7 (V7) ±3 Days after EOT Visit) (28 days : **End of Study**

Figure 3-1: Study Schematic

CONFIDENTIAL Page 44 of 108

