The following assessments will be performed at V3, V4, and V5/EOT: physical examination, vital signs, clinical status – ordinal scale assessment, PaO2/FiO2 measurement, pulse oxygen saturation (SpO2), positive end-expiratory pressure (PEEP) (for intubated subjects), sequential Organ Failure Assessment (SOFA) score, NEWS2 assessment, nasopharyngeal swab sample collection, health status assessment on an ordinal scale, assessment for the requirement of: mechanical ventilation, non-invasive ventilation, supplemental oxygen, vasopressors use, renal replacement therapy, ICU admission and hospital stay, assessment for any new infections, and laboratory sample collection for routine serum biochemical, hematologic, coagulation, serum/urine pregnancy test (V5/EOT), urinalysis, CD3+, CD4+ and CD8+ T cell count, CCR5 receptor occupancy for Treg and macrophage, serum cytokine and chemokine levels, and CCR5 gene polymorphisms.

[figure not shown]
Additionally, a chest radiograph or CT (if clinically indicated), mortality assessment, and ECG will be performed at V5/EOT visit. Adverse events and medications will be monitored throughout the study.

[figure not shown]
Follow Up Period (2 and 4 weeks after EOT± allowed windows)

Follow-up visits will be performed at 2 weeks (V6) and 4 weeks (V7) after the End of Treatment (EOT) visit. In order to ensure the safety of subjects and site staff, follow-up visits can be conducted as telephone or video contact visits.

The following assessments will be performed at V6 and V7 visit: review of adverse events and concomitant medications, physical examination, vital signs, clinical status – ordinal scale assessment (V6 only), nasopharyngeal swab sample collection, mortality status, and blood collection for routine serum biochemical, hematologic, coagulation and urine laboratory assessments (V7 only). If V7 is a telephone/video visit, the scheduled blood sample collection will

CONFIDENTIAL Page 49 of 108

not be performed. In such cases, missed blood sample collection will not be captured as protocol deviation.

Note: During visits conducted at the study clinic, subjects and site personnel will use appropriate protective gear (e.g., masks, gloves) to prevent the spread of the infection. If the subject is discharged from the hospital prior to Visit 7 (Day 42), scheduled study visits can be conducted by a visiting nurse (or trained site staff) at the subject's home to mitigate the risk of spreading COVID-19.

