Assessment for the requirement of: Mechanical Ventilation, Non- Invasive Ventilation, Supplemental Oxygen, Vasopressors Use, Renal Replacement Therapy, ICU Admission and Hospital Stay	Х	х		х	х	х		
Assessment for any new infections		X		X	X	X		
Mortality Status						X	X	X
Concomitant Medications	X	X	X	X	X	X	X	X
Adverse Events			X	X	X	X	X	X

- [1] Informed consent must be obtained prior to patient participation in any protocol-related activities that are not part of routine care.
- [2] Initial evaluation of patient eligibility will be performed by Investigator.
- [3] Medical history and current therapies (medications and non-medications).
- [4] Symptom-directed physical examination
- [5] Post treatment vital signs will be recorded at V2, V4, V5 (EOT) and will include blood pressure, heart rate, respiration rate, and temperature.

CONFIDENTIAL Page 52 of 108

Date: 28-Dec-2020

- [6] The SOFA score assessment will be based on PaO2/FiO2, platelets, Glasgow coma scale (GCS), bilirubin, Mean arterial pressure OR administration of vasoactive agents required, and creatine.
- [7] National Early Warning Score 2 (NEWS2) Assessment is based on 7 clinical parameters (respiration rate, oxygen saturation, any supplemental oxygen, temperature, systolic blood pressure, heart rate, level of consciousness)
- [8] Based on hospital discharge or normalization of fever, respiratory rate, alleviation of cough, and resolution of hypoxia.
- [9] Hemoglobin, Hematocrit (HCT), Red Blood Cells (RBC), White Blood Cells (WBC) with total and differential count, Absolute Neutrophil Count (ANC) and platelets.
- [10] Biochemistry

Hepatic function indicators: total bilirubin, alkaline phosphatase, aspartate aminotransferase (AST), alanine aminotransferase (ALT), total protein, albumin Lactate dehydrogenase (LDH)

Renal function indicators: Serum creatinine, creatinine clearance, or eGFR

Electrolytes: sodium, potassium, chloride, calcium and bicarbonate

Other: glucose (random), cholesterol (total), Creatine kinase, C-reactive protein, serum ferritin, d-dimer

- [11] Prothrombin time (PT) and International Normalized Ratio (INR)
- [12] ONLY performed on women of childbearing potential.
- [13] Urine samples will be tested for color, appearance, specific gravity, pH, protein, glucose, occult blood, ketones, leukocyte esterase, nitrite, bilirubin, urobilinogen, and microscopic examination of urine sediment.

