4.3.1. Visits 6 and 7 (V6 and V7)

The assessments performed at these visits will include:

[figure not shown]
- Physical examination (see Section 7.5);
- Vital Signs (see Section 7.6),
- Clinical Status Ordinal scale assessment at Visit 6 only (see Section 7.10);
- Collection of blood specimens at Visit 7 only (see Section 7.8) for
 - Complete blood count;
 - Biochemistry;
 - Coagulation indices; and
 - Urine sample for urinalysis parameters.
- Nasopharyngeal Swab Sample Collection (See Section 7.18)
- Review of mortality status;
- Prior medications assessment (see Section 7.7); and
- Review of adverse events (see Section 9).

Note: The follow-up visits (V6 and V7) can be conducted as telephone or video contact visits. If V7 is a telephone/video visit, the scheduled blood sample collection will not be performed. In such cases, missed blood sample collection will not be captured as protocol deviation.

The following assessments are not applicable for the single arm, non-randomized, open-label phase of the study:

- National Early Warning Score 2 (NEWS2) Assessment
- Blood sample collection for
 - CCR5 receptor occupancy for Treg and macrophage
 - Serum cytokine and chemokine levels
 - CCR5 Gene Polymorphisms
- Nasopharyngeal Swab Sample Collection

CONFIDENTIAL Page 59 of 108

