7.19. CHEST RADIOGRAPH OR COMPUTED TOMOGRAPHY SCAN

If clinically indicated by the treating physician, a chest radiograph or CT scan will be performed at Screening Visit (V1) and V5 (EOT)

7.20. REQUIREMENT OF MECHANICAL VENTILATION, NON-INVASIVE VENTILATION, SUPPLEMENTAL OXYGEN, VASOPRESSORS USE, RENAL REPLACEMENT THERAPY, ICU ADMISSION, AND HOSPITAL STAY

The incidence and duration, in days, of mechanical ventilation, non-invasive ventilation, supplemental oxygen, vasopressors use, renal replacement therapy, ICU admission and hospital stay will be assessed at Screening (V1) and V3, V4, and V5 (EOT).

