14. DATA HANDLING AND RECORD KEEPING

14.1. RECORDING AND COLLECTION OF DATA

The primary source document for this study will be the subject's medical record. If separate research records are maintained by the Investigator(s), the medical record and the research records will be considered the source documents for the purposes of auditing the study.

Applicable source data will be manually transcribed to approve case report forms (CRF). The Investigator is ultimately responsible for the accuracy of the data transcribed on the forms. All source documents and CRFs will be completed as soon as possible after the subject's visit.

The Investigator will review the CRFs to indicate that, to his/her knowledge, they are complete and accurate. Designated source documents will be signed and dated by the appropriate study personnel. The Investigator must agree to complete and maintain source documents and CRFs for each subject participating in the study.

All research data will be entered, either electronically or manually, into a computerized database. The clinical database will be designed by the clinical data manager in accordance with 21 CFR Part 11 and based on protocol requirements defined by the Sponsor in association with the Lead Investigator.

The Investigator will maintain a confidential list of study subjects that will include each subject's study number, name, date of birth, and unique hospital identification number if applicable. This list will be kept by the Investigator and will not be collected by the Sponsor. A notation will be made in the subject's case history/medical chart that he/she is participating in a clinical study and has provided a signed and dated ICF as well as a release for protected health information as required by local policies. The Investigator must also maintain a separate screening log of all the subjects screened for participation in the study; it should include gender, age, eligibility status, reason for ineligibility, if applicable; and study allocated subject number, if applicable.

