#### 5.2.8 Data Provided to DSMC

The DSMC will receive a statistical report. The report will include disposition, demographics, mortality data and safety summaries. Besides the mortality data, the report will also include descriptive summary of key outcome indicators such as, change in clinical status based on a 7 point ordinal scale and total duration of hospitalization, ICU, and mechanical ventilation use.

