### 8.3 Handling of Missing Data

Every effort will be made to obtain required data at each scheduled evaluation from all subjects who have been randomized to minimize missing data. However, in the event when there is missing data the following imputation methods will be used.

For efficacy evaluations, multiple imputation methods will be used to handle missing data. This imputation method is a robust method to impute missing measurements. The method for imputing variables is available in SAS PROC MI for both monotone and arbitrary missing data patterns and will be implemented with the PREDICT MEAN MATCHING option. Each imputation model will include the stratification factor as a covariate in the model. The multiple imputation is used for subjects that have some baseline and post-baseline data, i.e., if a subject is missing all pre and post baseline data, no data will be imputed.

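### Length of hospital stay: the duration record is scheduled only to V5, and the SAP's Day 42 rule for deaths leaves survivors' open or long stays without a score

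*Protocol*

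**What the plan says.** **Endpoint and test.** Length of hospital stay is a secondary endpoint (Protocol 8.2.2, SAP 3.2). SAP 8.4 tests the secondary endpoints in a fixed sequence in the order of SAP 9.2.2, where length of stay is the fourth and last. SAP 9.2.2.4 compares medians by a non-parametric method or rank-ANCOVA.

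**Collection.** Protocol 7.20 covers incidence and duration of these items: "renal replacement therapy, ICU admission and hospital stay will be assessed at Screening (V1) and V3, V4, and V5 (EOT". The matching row of Table 4-2, which ends "Renal Replacement Therapy, ICU Admission and Hospital Stay", also marks V2 and is blank at V6 and V7. Protocol 4.3.1 introduces its V6/V7 list with "The assessments performed at these visits will include", and the item is not on the list. The Section 4 narrative gives for the same visits "ordinal scale assessment (V6 only), nasopharyngeal swab sample collection, mortality status, and blood collection for routine serum biochemical". After V5, then, the scheduled items that bear on hospital status are the ordinal scale at V6 and mortality status at V6 and V7.

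**Scoring.** SAP 8.7.4 places every death within 42 days at Day 42, as the worst rank, and says any later time would give the same result. The rule also applies to ICU stay and ventilation duration. It covers deaths only. SAP 9.2.2.4 refers to the rule as Section 8.6.4, but SAP 8.6 has no subsections. Neither document says whether a stay starts at admission or at Day 0.

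**Missing data.** SAP 8.3: "For efficacy evaluations, multiple imputation methods will be used to handle missing data". SAP 8.3.1 uses predictive mean matching for continuous variables and states no bound.

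**The concern.** The analysis places deaths at Day 42, while the scheduled duration record ends 26 to 30 days earlier. Some survivors will still be in hospital at V5, and some may be at Day 42. The SAP says nothing about the value they receive, so it would have to be chosen at analysis.

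Two choices follow that can change the result. The first is how a survivor with a very long stay ranks against a patient who died. The second is whether an open stay counts as missing and, if so, what may be imputed. Left open until after unblinding, both put analyst discretion into a test that belongs to the controlled sequence.

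**Working it through.** **1. The plan's own figure.** The documents give no power figure for length of stay. The only design calculation is for Day 28 mortality, 45% versus 30%, 2:1, two-sided 0.05, 80% power. The unpooled Z formula gives (0.45×0.55 + 0.30×0.70/2) × (1.960 + 0.842)² / 0.15² = 123 placebo patients, hence 246 + 123 = 369. This reproduces the plan and is not affected here. The two mortality rates are used below.

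**2. Visit windows.** V4 is 7±1, so Day 6 to 8. V5 is V4 + (7±1), so Day 12 to 16. V6 is V5 + (14±3), so Day 23 to 33. V7 is V5 + (28±3), so Day 37 to 47. From V5 to Day 42 is 42−16 = 26 to 42−12 = 30 days.

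**3. Does any value from Day 42 onward keep deaths worst?** Only if every survivor's stay is below 42 days. A survivor at exactly 42 ties with deaths placed at 42, and a longer stay ranks worse than death. Both can occur. V7 can be as late as Day 47. Counted from admission, a patient admitted 7 days before Day 0 and discharged on Day 36 has a stay of 43 days.

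**4. What would predictive mean matching return?** It copies observed values. Counted from Day 0 on the scheduled record alone, donors have either a completed stay of at most 16 days or the death value 42, so nothing can fall on 17 to 41. With assumed survivor medians of 8 to 20 days (log-SD 0.7) and deaths as donors, 34% to 58% of imputed stays were at or below the days already observed and 40% to 63% equalled 42. With survivor donors only, 91% to 96% were at or below the days already observed. Counted from admission, with an assumed 0–6 or 0–10 days in hospital before Day 0, about 5–6% or 12–14% of imputed values did fall on 17 to 41.

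**5. Power of the rank test.** The documents give no stay distribution. Assumed: 260/130 patients, log-normal survivor stays (log-SD 0.8) rounded up to whole days, tie-corrected Mann-Whitney test at two-sided 0.05, 5,000 runs (Monte Carlo error about 0.7 points). Power in %:

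| Mortality, leronlimab/placebo | Placebo median stay; leronlimab stay | Full record, deaths at 42 | Full record, deaths above 42 | V6 bracket, deaths worst | Open stays tied after Day 14, deaths worst |
|---|---|---|---|---|---|
| 30/30 | 10; 25% shorter | 39 | 36 | 36 | 34 |
| 30/30 | 16; 25% shorter | 45 | 36 | 34 | 29 |
| 30/30 | 20; 35% shorter | 81 | 67 | 63 | 51 |
| 35/35 | 20; 35% shorter | 71 | 53 | 48 | 38 |
| 30/45 | 10; equal | 67 | 70 | 70 | 71 |
| 30/45 | 16; equal | 60 | 69 | 70 | 72 |
| 30/45 | 20; equal | 55 | 70 | 70 | 73 |

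The V6 bracket splits stays open at Day 14 into discharged by Day 28 or still in hospital.

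- Deaths at 42 instead of above 42: from 71−53 = +18 to 55−70 = −15 points.
- Missing dates with deaths kept worst, equal mortality: a loss of 0 to 53−48 = 5 points with the V6 bracket, and 2 to 67−51 = 16 with ties.
- Missing dates at design mortality with equal stays: power changes by 0 to +3 points.
- Design mortality with shorter stays: 95% to 99.7% in all four records.
- Type I error with ties: 4.5% to 5.4%.

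**6. Medians.** With 45% deaths, the placebo median passes Day 14 once more than 50−45 = 5% of placebo patients are alive in hospital then; for leronlimab at 30% deaths, more than 20%. For survivor median 10, 0.55 × 0.337 = 18.5% of placebo patients are alive in hospital at Day 14. The placebo median is the 0.50/0.55 = 0.909 quantile of survivor stays: 10 × exp(0.8 × 1.335) = 29 days (31 in the simulation, with whole days). With design mortality and equal stays, the difference in medians is about 15 days on the full record (31 versus 16). After imputation it is about 25 with deaths as donors (38 versus 12), about 17 if V6 hospital status is also in the model, and about 6 with survivor donors only.

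**The case against.** The strongest reply is that the dates probably exist. Protocol 14.1 says "The primary source document for this study will be the subject's medical record". SAP 5.2.8 has the DSMC receive "total duration of hospitalization, ICU, and mechanical ventilation use" at an interim analysis timed at four weeks. Home visits up to Day 42 require sites to know who has been discharged. The CRF is not among the documents. This stands: a reader might infer that stays after V5 are unrecorded and the endpoint cannot be computed, and the documents do not support that. They show only that the protocol does not schedule the item after V5.

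Second, the SAP does not call an open stay missing, so imputation is one possible route and not the stated one. A reader might infer that imputation necessarily widens the difference in medians, or can never yield a stay of 17 to 41 days. Neither holds in general: the first depends on the donor pool and the covariates, the second on counting from Day 0.

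Third, the schedule gap costs little once the V6 score is used, and the largest power shifts come from scoring at Day 42. That is right, and the scoring rule is the main repair. It does not remove the point: even with every date in hand, SAP 8.7.4 leaves long-stay survivors unscored and its claim about the rank of deaths fails for them.

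Fourth, extending the visit schedule is probably too late for randomized patients. Protocol 3 says: "A single arm, non-randomized, open-label phase is added to the protocol after completion of enrollment in the Randomized Phase of the study". This is accepted, and the remedy relies on chart retrieval.

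**Conclusion.** The point holds as a gap in scoring and scheduling, of minor to moderate size. Independent of any assumed stay distribution: the duration item is scheduled only to V5, survivors with open stays have no stated value, the SAP's statement about values from Day 42 onward fails once a survivor's stay reaches 42 days, predictive mean matching as written has no floor, and the cross-reference is wrong.

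The sizes rest on assumed log-normal stays and can go either way: up to about 18 points of power from the rank given to deaths, 0 to 5 points from missing dates with the V6 score used and up to about 16 without it, and a shift in the medians whose direction depends on the donor pool.

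A reader might go further and infer that the trial's main conclusion is at risk. It is not. Day 28 mortality does not use this rule, the simulated type I error of the stay test remains near 5%, and no later confirmatory test depends on this endpoint.

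**What to change.** - **Dates.** Before unblinding, retrieve discharge, readmission, ICU and ventilation dates through Day 42 from the chart for all randomized patients. Where V7 fell before Day 42, confirm Day 42 status from the chart. Add the row to V6 and V7 (Table 4-2, Protocol 4.3.1 and 7.20) only for patients with those visits still to come.
- **SAP 8.7.4.** Define the stay as Day 0 to Day 42, score survivors still in hospital at Day 42 at 42, and rank deaths above 42. Apply the same rule to ICU stay and ventilation duration.
- **Open stays at loss or withdrawal.** Treat them as at least the days already observed, and use the V6 ordinal score where available.
- **SAP 9.2.2.4.** Correct the reference from 8.6.4 to 8.7.4.

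The cost is chart-retrieval effort and SAP wording. Ranking deaths above 42 lowers power in some scenarios (71% to 53% in one row above) and raises it in others (55% to 70%). The reason to adopt it is that it delivers the worst rank for death that the SAP says it intends.

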7.21. RANDOMIZATION

Subjects who are eligible to participate in the trial will be randomized to one of the treatment groups via IWRS (Interactive Web Based Randomization System) at Visit 2 prior to IP administration. The randomization will be central with a 2:1 ratio of Active Treatment to Control Treatment to ensure even distribution of Active and Control subjects.

CONFIDENTIAL Page 75 of 108

8. STATISTICAL ANALYSIS

This section presents general information about statistical considerations and concepts and a brief discussion on analysis methodology, as well as some data conventions. Detailed descriptions of the statistical analysis methods and data conventions that will be used in this study will be in a separate document; i.e., the Statistical Analysis Plan (SAP).

8.1. TREATMENT GROUPS

There will be two treatment groups in the study:

- 700 mg Leronlimab (PRO 140)
- Placebo

8.2. DESCRIPTION OF STUDY OUTCOMES (ENDPOINTS)

8.2.1. Primary Endpoint

The primary endpoint for the study is:

• All-cause mortality at Day 28

Note: Day 0 refers to the date of randomization/first treatment.

8.2.2. Secondary Endpoints

[figure not shown]
The secondary efficacy endpoints for the study are:

- All-cause mortality at Day 14
- Proportion of patients achieving a category of 6 or higher at Days 14 and 28 (on a 7 point ordinal scale).
- Change in clinical status of subject at Days 14 and 28 (on a 7 point ordinal scale)
 - A 7-category ordinal scale of patient health status ranges from: 1) Death; 2) Hospitalized, on invasive mechanical ventilation or extracorporeal membrane oxygenation (ECMO); 3) Hospitalized, on non-invasive ventilation or high flow oxygen devices; 4) Hospitalized, requiring supplemental oxygen; 5) Hospitalized, not requiring supplemental oxygen; 6) Not hospitalized, limitation on activities; 7) Not hospitalized, no limitations on activities.
- Length of hospital stay (days)

8.2.3. Exploratory Outcome Measures (Endpoints)

- All-cause mortality at Day 42
- Change in clinical status of subject at Days 3 and 7 (on a 7 point ordinal scale)

CONFIDENTIAL Page 76 of 108

A 7-category ordinal scale of patient health status ranges from: 1) Death; 2) Hospitalized, on invasive mechanical ventilation or extracorporeal membrane oxygenation (ECMO); 3) Hospitalized, on non-invasive ventilation or high flow oxygen devices; 4) Hospitalized, requiring supplemental oxygen; 5) Hospitalized, not requiring supplemental oxygen; 6) Not hospitalized, limitation on activities; 7) Not hospitalized, no limitations on activities.

- Change from baseline in Sequential Organ Failure Assessment (SOFA) score at Days 3 and 7.
- Proportion of subjects extubated within 14 days of start of study treatment.

 Note: This applies only for subjects who were intubated at the time of randomization
- Proportion of subjects admitted into an intensive care unit (ICU) after randomization

 Note: This applies only for subjects who were hospitalized but not in an intensive care unit

 (ICU) at the time of randomization
- Proportion of subjects requiring initiation of mechanical ventilation after randomization

 Note: This applies only for subjects who does not require mechanical ventilation at the time of randomization
- Change from baseline in Sequential Organ Failure Assessment (SOFA) score at Day14.
- Length of ICU stay (days)
- Duration (days) of mechanical ventilation (if applicable)
- Time to clinical recovery
- Time from initiation of the study to discharge or to normalization of fever (defined as <36.6°C from axillary site, or < 37.2°C from oral site or < 37.8°C from rectal or tympanic site), respiratory rate (< 24 bpm while breathing room air), alleviation of cough (defined as mild or absent in a patient reported scale of 0=absent, 1=mild, 2=moderate, and 3=severe) and resolution of hypoxia (defined as SpO2 ≥ 93% in room air or P/F ≥ 300 mmHg). All these improvements must be sustained for at least 24 hours.
- Change from baseline in pulse oxygen saturation (SpO2) at Days 3, 7, and 14
- Change from baseline in National Early Warning Score 2 (NEWS2) at Days 3, 7, and 14.

 This score is based on 7 clinical parameters (respiration rate, oxygen saturation, any supplemental oxygen, temperature, systolic blood pressure, heart rate, level of consciousness).
- Incidence of transaminitis, defined as an increase in alanine aminotransferase (ALT) and/or aspartate aminotransferase (AST) to > 5 times the upper limit of normal.
- Incidence of subjects requiring Renal Replacement Therapy (RRT) after randomization

CONFIDENTIAL Page 77 of 108

- Incidence of new bacterial, invasive fungal, or opportunistic infection
- Change in size of lesion area by chest radiograph or CT
- Change from baseline in serum cytokine and chemokine levels at Days 3, 7, and 14
- Change from baseline in CCR5 receptor occupancy levels for Tregs and macrophages at Days 3, 7, and 14
- Change from baseline in CD3+, CD4+ and CD8+ T cell count at Days 3, 7, and 14

